6.3.4 Per-Protocol (PP) population

The Per Protocol (PP) population consists of all subjects in the ITT population who have completed all 10 visits with no missing ADHD-RS-5 assessments and no major protocol violations. Subjects will be analyzed according to the treatment they received.

The analysis population will be indicated as a subtitle in each table, listing and figure.

6.4 Subject Disposition

A disposition of subjects will include the number and percentage of subjects in each of the following categories:

- Subjects in the randomized population
- Subjects in the safety population
- Subjects in the ITT population
- Subjects in the PP population

Within each of the previous categories, the number and percentage of subjects who completed, early discontinued and the reason for early discontinuation from the study will be summarized in Table 14.1.1.1. The reason for early discontinuation may include any of the following:

- Subject withdrew consent
- Lost to follow-up
- Administrative reason
- Adverse event
- Investigator decision
- Failure to follow required study procedures
- Other

Subject randomization schedule will be listed. Subjects whose randomization codes are unblinded during the conduct of the study will be listed along with the reason for un-blinding (Listing 16.1.7).

Subject disposition for screened subjects will be presented in Table 14.1.1.2. Subject enrollment distribution by site will be presented for the ITT population in Tables 14.1.1.3.

Data listing will be presented for subject disposition among all randomized subjects (Listing 16.2.1.1), screen failure among screened subjects (Listing 16.2.1.2), subject visit status at each visit (Listing 16.2.1.3), and visit dates (Listing 16.2.1.4) among all randomized subjects. Subject's inclusion and exclusion criteria response will be listed (Listings 16.2.2.1 - 16.2.2.2).

6.5 Protocol Deviations

The date of and reason for protocol deviations will be documented in all cases. Major protocol deviations will include the following but not limited to:

- 1) Subjects enrolled in the study but did not meet the inclusion/exclusion criteria.
- 2) Subjects who missed doses as per the treatment he was randomized to.
- 3) Subjects who received non-randomized medication.
- 4) Subject's treatment compliance < 80% or > 120%.

Major protocol violations will be finalized before the database lock and will be added to the above list.

Protocol violations will be summarized in Table 14.1.1.4.

Subjects with major protocol deviations will be listed based on all randomized subjects. The listing will include a brief description of the deviation, deviation category, and if applicable, study day when deviation occurred along with other pertinent information (Listing 16.2.2.3).

6.6 Handling Missing Data

6.6.1 Missing Efficacy Variables

Missing items in ADHD-RS-5 scale

1. If more than 3 items of ADHD-RS-5 have missing or invalid data, the total score will be set to missing. If the total score is missing then both subscales (inattention or Hyperactivity/Impulsivity) will be set to missing.
2. If 3 items of ADHD-RS-5 or less have missing or invalid data, the values for the missing items will be imputed using the mean of the non-missing items rounded to the nearest integer.

With respect to the primary analysis, missing ADHD-RS-5 Total Scores will be assumed to be missing at random (MAR) (*See Panel on Handling Missing Data in Clinical Trials, (2010) National Research Council: The Prevention and Treatment of Missing Data in Clinical Trials*) that is, given the observed data, the reason for the missing data does not depend on the unseen data. The Mixed Model for Repeated Measures (MMRM) method, implemented via SAS® PROC MIXED (SAS/STAT Software), will be used for handling missing ADHD-RS-5 Total Scores under MAR assumption. The motivation behind MMRM is to solve the issue of addressing an on-treatment question, i.e. what happens if a typical subject completes their assigned treatment. MMRM does this by conditioning on the previous observations and other covariates that may inform on both missingness and outcome.

A sensitivity analysis will be performed by assuming missing ADHD-RS-5 Total Scores are not missing at random (MNAR) ([Yang, 2014](#)), that is, the probability that an observation is missing may depend on its underlying unobserved value. This will be implemented using SAS® PROC MI and SAS® PROC MIANALYZE (SAS/STAT Software).

For secondary endpoints, missing values will be assumed as missing at random (MAR). Missing data will be imputed using SAS® PROC MI (SAS/STAT Software).

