3.5 Sample Size and Power Considerations

Seventy-two subjects per treatment group in the ITT population will yield 90% power at a significance level of 0.05 (two-sided) using a two-sample t-test with equal allocation to the treatment

groups. This assumes an effect size of 0.547, observed in the comparison of SPN-812 200 mg and placebo in the SPN-812 Phase IIb study (based on the CFB to endpoint in the ADHD-RS-IV total score). A total of 300 subjects (100 subjects in each of the three treatment groups) will be randomized to account for an anticipated 27.9% of randomized subjects not completing the study.

4 Definitions and Derivations

1. Baseline: Unless specified otherwise, baseline is defined as the non-missing value collected most recent to and before the time of the very first dose of the SM.
2. The study day (DY) is calculated as Visit date minus Reference date + 1 day if the visit date occurs on or after the reference date or Visit date minus Reference date if the visit date occurs before the Reference date, where the Reference date is defined as the first dose date (DY=1)
3. The change from baseline at a given Visit = observed value at that Visit minus observed value at baseline
4. ADHD-RS-5 total score =sum of scores for the 18 behaviors
5. ADHD-RS-5 Inattention subscale score = sum of scores for the first 9 behaviors
6. ADHD-RS-5 Hyperactivity/Impulsivity Subscale score = sum of scores for the last 9 behaviors
7. Conners 3-Parent Reported score: Composite T-score calculated by averaging over the 6 domains
8. Conners 3-Parent Reported score: T-score for individual domain: inattention, hyperactivity/impulsivity, aggression, executive functioning, learning problems, and relationships
9. Conners 3-Self Reported score domains: Composite T-score over the 5 domains
10. Conners 3-Self Reported score domains: inattention, hyperactivity/impulsivity, aggression, learning problems, and relationships
11. WFIRS-P score=average of all 50 items
12. WFIRS-P subscale scores: average of items of following 6 subdomains: Family, School (learning and behavior), Life Skills, Child's Self-Concept, Social Activities, and Risky Activities
13. PSI-4-SF: score=sum of all 36 items
14. PSI-4-SF: subscale scores: sum of items of following 3 subdomains: parental distress (PD), parent-child dysfunctional interaction (P-CDI), and difficult child (DC)

5 Study Variables

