6.14 Analysis of Secondary Endpoints

All secondary analyses are based on the ITT population with missing values imputed at week 8 (WK8) using multiple imputation (MI) assuming MAR using SEED=2460650. In case imputed values are below or above the range of the applicable scale, values will be imputed to respectively the minimum or maximum value of the scale. The following SAS code will be used MI.

```
PROC MI DATA=EFF NIMPUTE=100 SEED=2460650 OUT=MIOUT;  
  CLASS TREATMENT;  
  VAR TREATMENT BASELINE WK8(EOS);  
  FCS REG;  
RUN ;
```

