6.14.2.3 ADHD-RS-5 Hyperactivity/Impulsivity and Inattention Subscales

The change from baseline to EOS in ADHD-RS-5 Inattention and the change from baseline to Week 8 (EOS) in Hyperactivity/Impulsivity subscales will be analyzed using ANCOVA model with fixed effects for treatment, age group and baseline as a covariate. Each of the treatment groups (SPN-812 ER 200 mg and 400 mg) will be compared with the Placebo. The p-values, LS means of treatment groups, differences between the LS means and placebo will be presented. The summary of this analysis will be presented in Table 14.2.2.3.

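### SAP 6.6.1 discards a fully answered Week 8 ADHD-RS-5 subscale whenever the 18-item total is missing, yet keeps a subscale with 3 of its 9 items filled in

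*SAP*

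**What the plan says.** Section 6.6.1 gives two item-level rules for the ADHD-RS-5. Rule 1 begins: "If more than 3 items of ADHD-RS-5 have missing or invalid data, the total score will be set to missing". It continues: "If the total score is missing then both subscales (inattention or Hyperactivity/Impulsivity) will be set to missing". Rule 2 covers the remaining forms: "If 3 items of ADHD-RS-5 or less have missing or invalid data, the values for the missing items will be imputed using the mean", taken over the answered items and rounded to an integer. Neither rule counts missing items within a subscale.

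Section 4 defines the scores. For the whole form it gives "ADHD-RS-5 total score =sum of scores for the 18 behaviors". For the first half it gives "ADHD-RS-5 Inattention subscale score = sum of scores for the first 9 behaviors", and for the second half "ADHD-RS-5 Hyperactivity/Impulsivity Subscale score = sum of scores for the last 9 behaviors".

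Section 6.14.2.3 analyses the two subscales separately, as additional secondary endpoints. The change from baseline to Week 8 in the "subscales will be analyzed using ANCOVA model with fixed effects for treatment, age group and baseline as a covariate".

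Section 6.14 handles missing Week 8 values of secondary endpoints by multiple imputation under MAR, with 100 imputations. The variable list in the code is "VAR TREATMENT BASELINE WK8(EOS"), that is, treatment, baseline and the Week 8 value. Neither the answered items nor the visits between baseline and Week 8 are listed.

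**The concern.** Whether a subscale can be used is decided by a count over all 18 items, nine of which do not belong to it. A Week 8 subscale score that is fully known from the form can therefore be treated as unobserved and redrawn by a model that ignores the answers on that form. At the same time a subscale with a third of its own items blank is accepted. What is at stake is some precision in two separately analysed secondary endpoints. In the by-visit descriptive summaries planned in section 6.13, the discarded score would simply be absent.

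**Working it through.** The SAP gives no figure on this point to reproduce. The check applies the two rules literally and then counts patterns.

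**Inputs.** 18 items in two subscales of 9 (section 4). The total is missing if more than 3 items are missing or invalid, and both subscales are then missing; with 3 or fewer, the items are filled (section 6.6.1). Week 8 imputation uses treatment and baseline (section 6.14).

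**Rules applied.** Write (a, b) for a blank Inattention items and b blank Hyperactivity/Impulsivity (H/I) items.

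| Pattern | Total | Inattention | H/I |
|---|---|---|---|
| (4, 0) | missing | missing (5 of 9 answered) | missing, although 9 of 9 answered |
| (9, 0) | missing | missing (0 of 9 answered) | missing, although 9 of 9 answered |
| (2, 2) | missing | missing (7 of 9 answered) | missing (7 of 9 answered) |
| (3, 0) | scored | kept, 3 of 9 items (33%) filled | kept, 9 of 9 answered |

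A complete subscale is lost in every pattern (k, 0) or (0, k) with k from 4 to 9. No section restores it.

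**How often, per affected form.** Assume exactly 4 blanks at random positions. The number of possible placements is C(18,4) = 3060.

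- (4, 0) or (0, 4), one subscale complete: 2 × C(9,4) = 2 × 126 = 252; 252/3060 = 8.2%.
- (3, 1) or (1, 3): 2 × C(9,3) × 9 = 2 × 84 × 9 = 1512; 1512/3060 = 49.4%.
- (2, 2): C(9,2)² = 36² = 1296; 1296/3060 = 42.4%.
- Check: 252 + 1512 + 1296 = 3060.

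If the blanks instead cluster in one half of the form, as when a block of questions is skipped, the share with one complete subscale rises towards 100%.

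These are shares of forms that already have 4 blanks. The SAP gives no item-missing rate, so the number of such forms cannot be computed.

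**Comparison within the SAP.** Section 6.14.1.3 scores each WFIRS-P domain from its own answered items, leaving out missing ones. The document therefore does not apply one whole-form convention to every multi-domain scale.

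**The case against.** The strongest reply is that this is a scoring convention and not an error. Section 4 says how a score is summed and section 6.6.1 says when a form is too incomplete to score, so the two do not contradict each other. The rule is explicit, is the same in all arms, and keeps the total equal to the sum of the two subscales in the same subjects. The scale is administered and scored by the investigator (section 5.1), so forms with four or more blanks may be rare or absent. All of this stands, and it limits the size of the point. It does not give a reason to discard a subscale whose nine items were all answered.

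Three stronger readings are tempting, and the documents do not support them.

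- **A large error in the result.** Take, as assumptions, a subscale SD of 7 and a baseline to Week 8 correlation r of 0.3 to 0.6. One imputed draw then differs from the true value with SD 7 × √(2(1 − r²)), about 9.4 to 7.9 points. The estimate, however, averages 100 imputations. The error it carries is 7 × √((1 − r²)(1 + 1/100)), about 6.7 to 5.6 points for that child. In an arm of 100, one such child moves the mean by about 0.06 to 0.07 points.
- **Baseline scores are replaced too.** The text of section 6.14 imputes at Week 8. Baseline is the latest non-missing pre-dose value (section 4), the scale is also scheduled at screening (Table 1), and the ITT population requires a baseline assessment (section 6.3.3).
- **The rule cannot reduce bias.** A form with many missing or invalid items might be unreliable as a whole. The documents settle this neither way, so the case rests on precision alone.

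**Conclusion.** The point holds as a minor one. Read literally, rule 1 discards a complete Week 8 subscale when four or more items are missing in the other half of the form, and section 6.14 then imputes it from treatment and baseline only. Rule 2 meanwhile keeps a subscale with 3 of 9 items filled in.

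The consequence is a small, avoidable loss of precision in two additional secondary endpoints. These lie outside the primary and key secondary endpoints for which multiplicity is controlled, and the primary total-score analysis is unaffected. The 8.2% rests on exactly four blanks at random positions, and the rise towards 100% on blanks clustering in one half. How many subjects are affected is unknown and could be none.

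**What to change.** Leave the total-score rule and rule 2 of section 6.6.1 as they are. Replace the second sentence of rule 1 with:

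> *If the total score is missing, a subscale with all 9 of its own items answered is still scored as the sum of those items; a subscale with any missing item is then set to missing.*

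Here an invalid item counts as missing, as it does in rule 1. Only subscales missing under this rule go to the imputation in section 6.14.

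The cost is one sentence and one derivation line. In a few subjects a subscale will be analysed although the total is missing.

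The change is deliberately narrow. Patterns such as (2, 2) or (3, 1) still lose both subscales. Setting a separate limit on missing items per subscale, for example 1, would recover more. However, it would clash with rule 2, which fills three blanks in one subscale and scores the total. It would also need a fill method for single blanks when the total is missing, which rule 2 does not supply.

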5.1 Primary Efficacy Variable

The ADHD-RS-5 is an ADHD-specific rating scale designed and validated to assess current ADHD symptomatology as described in the fifth edition of the Diagnostic and Statistical Manual of Mental Disorders (DSM-V). The scale consists of 18 items that directly correspond to the 18 DSM-V symptoms and are further subdivided into two subscales: Hyperactivity/Impulsivity and Inattentiveness ([DuPaul, 2016](#)). The ADHD-RS-5 scale rates the frequency and severity of each symptom on a 4-point Likert-type scale from 0 (none) to 3 (severe) and allows assessment of functional impairments linked to each symptom dimension. The ADHD-RS-5 rating scale is one of the most commonly used measures of drug efficacy in the treatment of ADHD and is the primary outcome measure for this study. The ADHD-RS-5 Home Version: Child instrument will be administered and scored by Investigator at each weekly visit from Baseline through EOS.

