6.14.2.2 Short form of the PSI-4 (PSI-4-SF)

PSI-4-SF consists of 36 items divided into three domains: parental distress, parent-child dysfunctional interaction, and difficult child, which is scored using a 5-point as 1 (Strongly disagree), 2 (Disagree), 3 (Not sure), 4 (Agree), 5 (Strongly agree). For Item-32, the subject's original response

categories from the Answer Sheet are rated as 1 = “much harder than I expected” to 5 = “much easier than I expected”. This will be reversed prior to calculating the subscale and total domain scores. The reversed Item-32 will be scored as from 5 = “much harder than I expected” to 1 = “much easier than I expected”.

Scores will be calculated if:

1. No more than 1 item is missing from any subscale

If the above criteria are met, then the missing data convention is:

1. Identify the domain from which the item response is missing
2. Compute the average raw score for the completed items within that subscale, and round the average to the nearest whole number.
3. Assign the rounded whole number score to the missing item and then the subscale score

Domains and Subscales:

1. Sum responses items 1-12 = **PD** - Parental Distress
2. Sum responses items 13-24 = **P-CDI** - Parental-Child Dysfunctional Interaction
3. Sum responses items 25-36 = **DC** - Difficult Child

Total Stress Score (TS) = PD + P-CDI + DC

The change from baseline in PSI-4 total score to Week 8 (EOS) will be analyzed using ANCOVA model with fixed effects for treatment and baseline as a covariate. Each of the treatment groups (SPN-812 ER 200 mg and 400 mg) will be compared with the Placebo. The p-values, LS means of treatment groups, differences between the LS means and placebo will be presented. The summary of this analysis will be presented in Table 14.2.2.2 and Listings 16.2.6.12 - 16.2.6.14.

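### Missing ADHD-RS-5 items are filled from a mean that names no subscale, which pulls the two separately analysed subscale scores toward each other (minor; free to fix)

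*SAP*

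**What the plan says.** SAP Section 6.6.1 sets two rules for incomplete ADHD-RS-5 forms.

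- Above the limit: "If more than 3 items of ADHD-RS-5 have missing or invalid data, the total score will be set to missing". The subscales follow the total: "If the total score is missing then both subscales (inattention or Hyperactivity/Impulsivity) will be set to missing".
- At or below the limit of three items: "the values for the missing items will be imputed using the mean of the non-missing items rounded to the nearest integer".

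Both rules count items over the whole instrument. Neither mentions a subscale when it describes the fill, and there is no separate limit on missing items per subscale.

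Section 4 defines the scores that receive the filled values: "ADHD-RS-5 total score =sum of scores for the 18 behaviors", "ADHD-RS-5 Inattention subscale score = sum of scores for the first 9 behaviors" and "ADHD-RS-5 Hyperactivity/Impulsivity Subscale score = sum of scores for the last 9 behaviors". Items run from 0 to 3 (Section 5.1), so each subscale spans 0 to 27 and the total 0 to 54. The total is the primary endpoint (6.13.1). Each subscale has its own ANCOVA as an additional secondary endpoint (6.14.2.3).

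For PSI-4-SF, Section 6.14.2.2 first identifies the domain of the missing item and then says "Compute the average raw score for the completed items within that subscale". It allows at most one missing item per subscale.

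**The concern.** The two ADHD-RS-5 subscales are scored and tested separately because a child can be high on one and lower on the other. A fill taken from all answered items ignores that difference. With three inattention items missing, the mean rests on 15 answers: 6 from inattention and 9 from hyperactivity/impulsivity. So 60% of the information comes from the other domain. A subscale with a third of its items missing (3 of 9) is still scored in this way.

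What is at stake is mainly the accuracy of the two subscale scores. The filled values also enter the total score, so it has to be checked whether the primary endpoint is affected. The SAP gives no reason for a less specific rule here than for PSI-4-SF.

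**Working it through.** The SAP gives no figure for item missingness or for domain profiles, so there is no stated number to reproduce. All profiles below are assumptions, chosen to show a range.

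**Formula.** Let k items (1 to 3) be missing in one subscale. Let a be the item mean of that subscale and h the item mean of the other.

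- Scale-wide fill: round(((9 − k)·a + 9·h) / (18 − k))
- Own-subscale fill: round(a)
- Error in that subscale, and in the total: k × (fill − a)

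**Single profiles, inattention items missing**

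| a | h | k | Scale-wide mean | Fill | Error | Own-subscale fill | Error |
|---|---|---|---|---|---|---|---|
| 3 | 0 | 1 | 24/17 = 1.41 | 1 | −2 | 3 | 0 |
| 3 | 0 | 3 | 18/15 = 1.20 | 1 | −6 | 3 | 0 |
| 3 | 1 | 3 | 27/15 = 1.80 | 2 | −3 | 3 | 0 |
| 2.4 | 0.6 | 1 | 24.6/17 = 1.45 | 1 | −1.4 | 2 | −0.4 |
| 2.4 | 0.6 | 3 | 19.8/15 = 1.32 | 1 | −4.2 | 2 | −1.2 |
| 2.33 | 2.0 | 3 | 31.98/15 = 2.13 | 2 | −0.99 | 2 | −0.99 |
| 2 | 2 | 3 | 30/15 = 2.00 | 2 | 0 | 2 | 0 |

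For the 3-versus-0 profile, missing hyperactivity/impulsivity items give the mirror image: +2 for one item and +6 for three. When the domains are close, the two rules give the same fill.

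**Average error over many children.** This is a simulation of 200,000 children. Assumed: between-child SD 0.45 per subscale on the item scale, correlation 0.5 between subscales, item SD 0.7, items rounded and limited to 0–3. Three items are missing. IA is inattention and H/I is hyperactivity/impulsivity.

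| Mean subscale scores (IA, H/I) | Where items are missing | Scale-wide: IA / H/I / total | Own-subscale: IA / H/I / total |
|---|---|---|---|
| 21.4, 9.3 | at random over 18 | −1.04 / +1.09 / +0.05 | +0.09 / +0.05 / +0.15 |
| 21.4, 9.3 | all in IA | −2.40 / 0 / −2.40 | +0.35 / 0 / +0.35 |
| 21.4, 9.3 | all in H/I | 0 / +2.44 / +2.44 | 0 / +0.25 / +0.25 |
| 20.7, 18.5 | at random over 18 | −0.22 / +0.17 / −0.05 | +0.08 / +0.06 / +0.14 |
| 20.7, 18.5 | all in IA | −0.50 / 0 / −0.50 | +0.32 / 0 / +0.32 |
| 20.7, 18.5 | all in H/I | 0 / +0.39 / +0.39 | 0 / +0.26 / +0.26 |

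With one missing item confined to one subscale, the unequal profile gives about 0.7 points under the scale-wide rule and under 0.1 under the own-subscale rule. The small remainder under the own-subscale rule comes from rounding to an integer.

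**Reading the results.** The subscale distortion appears even when items are missing at random. The total behaves differently: the two subscale errors have opposite signs and nearly cancel, unless the missing items cluster in one domain.

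**The case against.** The strongest reply has five parts.

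- **The text may be ambiguous rather than wrong.** It does not expressly exclude a within-subscale mean. That is fair. But both rules take the whole instrument as their unit, so the scale-wide reading is the natural one. If the other was meant, two programmers working independently under Section 7 could derive different scores, and the sentence still needs completing.
- **The primary endpoint is not shown to be biased.** A reader might infer that a flawed fill of the primary scale biases the primary result. The SAP does not support this. With items missing at random the total is off by about 0.05 of 54 points, which is less than the 0.15 under the own-subscale rule. The rule is also the same in every arm and at every visit. A biased treatment comparison would need item missingness or domain profile to differ by arm or between baseline and Week 8, and the SAP says nothing of the kind. This stands.
- **The within-subscale rule is not shown to be the only right one.** PSI-4-SF is a different instrument, and the WFIRS-P average in 6.14.1.3 is taken over answered items regardless of domain. What the ADHD-RS-5 scoring manual prescribes cannot be seen here. This stands as a limit, but it gives no reason to prefer a cross-domain fill for subscales that are analysed separately.
- **Rounding can hurt either rule.** With item means 2.5 and 1.0 and three inattention items missing, the scale-wide error is −1.5 and the own-subscale error +1.5. If the three missing items are hyperactivity/impulsivity items instead, the errors are +3 and 0. The advantage is on average, not in every child.
- **Few forms are affected.** The investigator administers and scores the scale (5.1), so one to three blank items should be uncommon. The subscales also lie outside the multiplicity-controlled sequence (6.13, 6.14.1). Both points stand and keep this minor.

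**Conclusion.** The point holds as a minor, practically free improvement to the subscale endpoints. As written, 6.6.1 mixes two domains that the SAP scores and tests separately, and it is inconsistent with the SAP's own PSI-4-SF rule.

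On an affected form with three missing items, the subscale error ranges from about 0.2 points on average (similar domains, random missingness), through about 1 point (unequal domains, random), to about 2.4 points (unequal domains, all in one subscale). The most extreme single profile reaches 6 of 27 points. These sizes depend on the assumed profiles and item spread. The frequency of such forms is not stated and is probably low.

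The total is materially wrong only for individual children or where missing items cluster in one domain. It would go too far to conclude that the primary analysis is biased. Sample size and power do not change.

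**What to change.** In Section 6.6.1, state that when three or fewer ADHD-RS-5 items are missing or invalid, each is replaced by the mean of the non-missing items of its own nine-item subscale (items 1–9 or 10–18), and keep the rounding rule explicit. The threshold of three items for the total can stay as it is. A missing-item limit per subscale, like the one for PSI-4-SF, is a possible addition but is not needed for this correction.

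The cost is a few words of SAP text and one line of derivation code, changed before database lock. No other analysis is altered.
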